9.2 Setting

9.2.1 Study Population

This study will comprise IVF/ICSI stimulation cycles and FET cycles linked to the same stimulation cycles among women who received rhFSH-alfa reference product, HP-hMG or rhFSH-alfa biosimilar products for COS. The countries of study are Denmark and Sweden. The study population will be identified using registers with comprehensive nationwide coverage. Hence, all eligible IVF/ICSI cycles among the entire female population in each country will be included and the results from the study are expected to be representative of that population.

Women aged 18 years or more at ovarian stimulation start during the study period will be identified as eligible for inclusion in the study from each country's IVF Register. Individual-level data will then be linked to the Prescribed Drug Register, the National Patient Register, and the Medical Birth Register to further determine eligibility and ascertain baseline characteristics and safety and pregnancy outcomes. More details on each register are provided in Section 9.4.

For inclusion, all stimulation cycles will be assessed on a set of inclusion and exclusion criteria. The overall study population will include all women with at least one IVF/ICSI stimulation cycle fulfilling all eligibility criteria. Analysis-specific selection criteria, depending on the outcome of interest, will also be applied (see Section 9.7.1).

For inclusion of a stimulation cycle in the study, women must fulfill all of the following inclusion criteria:

1. *Initiated IVF/ICSI stimulation cycle with rhFSH-alfa reference product, HP-hMG or rhFSH-alfa biosimilar product monotherapy for COS during the study period²*
2. *Aged 18 years or more at stimulation cycle index date*
3. *Female sex at stimulation cycle index date*

Stimulation cycles are not eligible for this study if any of the following exclusion criteria are fulfilled:

1. *History of 5 or more IVF/ICSI stimulation cycles prior to the stimulation cycle index date*
2. *Ovarian stimulation for the purpose of oocyte donation, oocyte storage, embryo donation, oncological or other medically indicated embryo storage³, or preimplantation genetic testing (PGT)*
3. *Non-availability of individual-level data on IVF/ICSI treatment, dispensed drugs and medical history for 36 months or more prior to and including the stimulation cycle index*

² For Sweden, inclusion of eligible women may be limited to 31 December 2019 because of Q-IVF data availability.

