9.2.3 Study Time Periods

The overall **study period** is from 2010 through 2020. Different start dates are defined based on which two drugs are compared and, for the comparison with rhFSH-alfa biosimilar products, which country is analyzed. The study period ends on 31 December 2020 (or last available data) for both study drug comparisons and countries. Homogeneity in patient management over time, market entry of the comparator drugs and register lag times determine the start and end dates of the study period:

- rhFSH-alfa reference product vs. HP-hMG:
 - o Denmark, Sweden: 1 January 2010 – 31 December 2020
- rhFSH-alfa reference product vs. rhFSH-alfa biosimilar products:
 - o Denmark: 26 March 2014 – 31 December 2020
 - o Sweden: 20 June 2014 – 31 December 2020

For Sweden, inclusion of eligible women may need to be restricted to 31 December 2019, considering study timelines (see Section 6) and the typical two-year lag time for data availability from the Swedish National Quality Registry of Assisted Reproduction (Q-IVF) (see Section 9.4.2).

The overall **index date** is the date when the woman's *first* eligible IVF/ICSI stimulation cycle started (defined as start of ovarian stimulation) in the study period. The **stimulation cycle index date** is the date when each stimulation cycle started. For FET cycles linked to an included stimulation cycle, the cycle start date is the Last Menstrual Period (LMP) date for natural FET cycles or the date hormonal stimulation (replacement) treatment was started for stimulated FET cycles, as recorded in each country's IVF register.

The **baseline period** is defined as the 36-month minimum period prior to and including the (stimulation cycle) index date. During this period, (cycle) eligibility will be determined, and baseline covariates assessed. The baseline period may include time before the age of 18 years, for women who had IVF/ICSI treatment specifically at the age of 18 years. All available data from the registers will be used to obtain information on important covariates. Baseline data from the national patient registers, however, will be limited to the period in which ICD-10 coding has been

used comprehensively in each country (starting from 1994 in Denmark and 1998 in Sweden). The exact length of the baseline period will therefore vary between cycles within the same patient.

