9.4.2 Sweden

The Swedish National Quality Registry of Assisted Reproduction (Q-IVF) is maintained by a regional health authority, the Region Västra Götaland, and has data since 2007. The Q-IVF covers virtually 100% of IVF treatments in the Swedish population (10.4 million in 2020). It contains information on all IVF and IUI records from all IVF clinics in Sweden (currently, 6 public and 13 private). The information in the register includes a range of patient characteristics, all IVF and insemination treatments and their results (including pregnancy outcome). Approximately 20,000 IVF treatments per year are included in the register. Between 1982 and 2006, data was directly reported to the National Board of Health and Welfare with only clustered data (*i.e.*, without personal identification numbers). The Q-IVF used to be updated on a yearly basis, with data on IVF treatments and treatment outcomes becoming available approximately 2 years after the treatment was performed. Starting from 2020, all participating clinics report data on a regular, more frequent basis (33). Data availability lag time may therefore be reduced. Access to the register data for scientific research is applied from the regional health authority, after a dialogue with the authority. Applications are reviewed by a steering committee of the register.

The Swedish Medical Birth Register (SMBR) is managed by the National Board of Health and Welfare and has data since 1973. The register covers 100% of pregnancies when the child is born (live or stillbirth) after the gestational age of at least 22 weeks since July 2008 (week 28 before July 2008). Thus, no data on elective terminations or spontaneous abortions are available and information on stillbirths is only available from the gestational week 22 onwards (week 28 before July 2008). The register contains information reported by reproductive care, covering the duration of pregnancy and the infant period. The information recorded includes data on the mother (e.g. maternal diagnoses and exposures during pregnancy, including drug use since 1995), the delivery and the neonatal care. The data for the previous calendar year is usually available in December. Access to the register data for scientific research is applied from the National Board of Health and Welfare through a standard application procedure.

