The Swedish National Patient Register (SNPR) is managed by the National Board of Health and Welfare. The register covers virtually 100% of the Swedish population (10.4 million in 2020). This register includes all inpatient care since 1987 (ICD-10 from 1998) and specialized outpatient care

from 2001 onwards. It does not cover primary care. The register contains information on, e.g., date of admission and discharge, medical department where the patient was treated, patient demographics, diagnoses and procedures. Diagnoses are coded to ICD-10. Procedures are based on the Nordic Classification of Surgical Procedures (NCSP) and the Nordic Classification of Medical Procedures (NCMP). The register is updated annually with a ca 7-9-month lag-time to data access. The register has increased the reporting frequency from healthcare unites to only monthly, and thus more frequent than annual updates of the register for research purposes and faster data access can be expected in the future. Access to the register data for scientific research is decided by the National Board of Health and Welfare through a standard application procedure and is assessed on a case-by-case basis.

The Swedish Prescribed Drug Register (SPDR) is managed by the National Board of Health and Welfare. It covers virtually 100% of the Swedish population (10.4 million in 2020) and contains data on all drugs prescribed to patients in both primary and secondary care. The register has data since July 2005 and is updated monthly. It contains information on all prescribed medicines dispensed by community pharmacies, e.g., date of prescribing and dispensing, brand name, ATC code, strength and package size of the drug, number of packages and DDDs dispensed, and speciality of the prescriber. The prescribed dose and/or the indication, however, are only available as an optional free-text instruction to the patient. Drugs provided at hospitals or medical clinics (i.e., in the inpatient hospital setting) are not included. The data for a specific month is available with ca 14-day lag-time. Access to the register data for scientific research is applied from the National Board of Health and Welfare through a standard application procedure and is assessed on a case-by-case basis.

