Set 4	Stimulation cycles with drug of interest aspirated on or before 30 November 2020 ⁺	Secondary objective 2	Oocytes retrieved per aspirated stimulation cycle
			Embryos cryopreserved per aspirated stimulation cycle
			Utilizable embryos per aspirated stimulation cycle
Set 5	Stimulation cycles with drug of interest initiated on or before 31 August 2020 ⁺	Secondary objective 8	OHSS
Set 6	Fresh and frozen embryo transfers linked to stimulation cycles with drug of interest occurring on or before 31 December 2020 ⁺	Secondary objective 2	Fresh embryos transferred
			Frozen embryos transferred
Set 7	Fresh and frozen embryo transfers linked to stimulation cycles with drug of interest occurring on or before 30 September 2020 ⁺	Secondary objective 3	Implantation rate
Set 8	Women who initiated their first-ever stimulation cycle with drug of interest on or before 31 December 2019	Primary objective	MC-CLBR
		Secondary objective 4	TTLB

CCPR: cumulative clinical pregnancy rate; CLBR: cumulative live birth rate; CPR: clinical pregnancy rate; COPR: cumulative ongoing pregnancy rate; FET: frozen embryo transfer; LBR: live birth rate; MC-CLBR: multiple-cycle cumulative live birth rate; OPR: ongoing pregnancy rate; OHSS: ovarian hyperstimulation syndrome; TTLB: time-to-live birth.

Notes:

*Should data on initiated cycles from the Swedish Q-IVF be available only through 31 December 2019, this analysis set will be adjusted to the same day and month in 2019.

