9.7.3.3 Rates and Numbers

The results of the study outcomes in the study cohorts will be estimated by calculating the outcome measures according to their definitions (see Table 7) in both original and IPTW-weighted study cohorts.

For the analyses of LBR, a woman may contribute up to one delivery resulting in live birth. For the analyses of CLBR, a woman may contribute several deliveries resulting in live birth per each stimulation cycle. The same principle applies to the analyses of clinical and ongoing pregnancies, *i.e.*, a woman may contribute several clinical and ongoing pregnancies for the analyses of CCPR and COPR, respectively.

For the analysis of MC-CLBR, where the woman is the unit of analysis, only the first occurrence of a live birth per woman within the first five stimulation cycles using the same study drug will be considered. The MC-CLBR analysis will be performed by cycle rank, *i.e.*, analyzed as the cumulative probability of a live birth up to and including the first, second, third, fourth and fifth stimulation cycle, respectively. The MC-CLBR analysis will be restricted to women who initiated their first-ever stimulation cycle during the study period.

In the assessment of MC-CLBR, it is assumed that women who did not return during the study period for another stimulation cycle after a failed attempt (*i.e.*, who did not have a live birth), did not have any live birth. Thus, for the main analysis, the MC-CLBRs will be calculated as conservative estimates (20). Optimal estimates will be provided in a sensitivity analysis restricted to the primary objective (see Analysis 2 Section 9.7.3.9).

Rates and numbers will be expressed as the rate or number per 100 units of observations with 95% CI.

Table 7. Definitions of outcome measures

Study objective	Outcome measure	Numerator	Denominator
Primary objective	LBR	Number of deliveries with at least one live birth after fresh embryo transfer	Initiated cycles with drug of interest
	CLBR	Number of deliveries with at least one live birth after one initiated stimulation cycle, including all fresh or frozen embryo transfers linked to that cycle	Initiated cycles with drug of interest
	MC-CLBR	Number of deliveries with at least one live birth after each initiated stimulation cycle in up to five cycles, including all fresh or frozen embryo transfers linked to each of those stimulation cycles	Women who initiated 1, 2, 3, 4 or 5 cycles with drug of interest

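### In the Swedish HP-hMG comparison, *first-ever* stimulation cycle in Set 8 can only mean first observed since 2007, giving 3 years of look-back at the 2010 start against 16 in Denmark

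*Protocol*

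**What the plan says.** Protocol section 9.7.1, Table 5, defines Set 8 as "Women who initiated their first-ever stimulation cycle with drug of interest on or before 31 December 2019". Section 9.7.3.3 repeats the restriction: "The MC-CLBR analysis will be restricted to women who initiated their first-ever stimulation cycle during the study period". Section 9.7.3.5 applies it to TTLB and uses stimulation cycle rank as the unit of time. MC-CLBR is also reported by cycle rank.

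Section 9.2.3 sets the study period for the HP-hMG comparison as "Denmark, Sweden: 1 January 2010 – 31 December 2020" and, for the Swedish biosimilar comparison, "Sweden: 20 June 2014 – 31 December 2020".

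Section 9.4.2 says that the Swedish IVF register (Q-IVF) "is maintained by a regional health authority, the Region Västra Götaland, and has data since 2007". For 1982 to 2006, "data was directly reported to the National Board of Health and Welfare with only clustered data", that is, without personal identification numbers. On the Swedish Prescribed Drug Register (SPDR) it says: "The register has data since July 2005 and is updated monthly". Section 9.4.1 dates the Danish IVF register from 1994.

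Two eligibility rules in section 9.2.1 bear on this. Exclusion 1 is "History of 5 or more IVF/ICSI stimulation cycles prior to the stimulation cycle index date". Exclusion 3, the 36-month data requirement, is applied as a residency test.

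**The concern.** A restriction to first-ever cycles can be checked only as far back as identifiable records go. In Sweden that is 2007. A woman treated only before 2007 who returns after 1 January 2010 appears in Q-IVF as a new patient. She enters Set 8 at rank 1, and previous failed stimulation, history of stimulation and previous live birth after IVF (Table 1) show nothing from Q-IVF for her. In Denmark the same woman would normally be recognised and left out of Set 8.

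Three things follow if the plan is carried out as written:
- Swedish Set 8 mixes true first cycles with some later ones, and both outcomes built on it depend on rank.
- The same label selects somewhat different populations in two countries whose results may be pooled (section 9.7.3.8).
- Exclusion 1 is undercounted in Sweden for the same reason.

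Nothing in the protocol deals with this. The 36-month criterion does not screen for older cycles. Section 9.9 does not list the truncation. No analysis in Table 8 varies the Swedish start date: analysis 3 moves the end date, and analysis 5b, the only later start, is for Denmark.

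**Working it through.** **1. Look-back by comparison.** Formula: look-back = opening date of the comparison − first date of person-level IVF data. Only the years 2007 and 1994 are given, so 1 January of each year is assumed.

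| Country and comparison | Opens | Person-level IVF data from | Look-back |
|---|---|---|---|
| Sweden, HP-hMG | 1 Jan 2010 | 1 Jan 2007 | 1,096 days = 3.0 years |
| Sweden, biosimilar | 20 Jun 2014 | 1 Jan 2007 | 2,727 days = 7.5 years |
| Denmark, HP-hMG | 1 Jan 2010 | 1 Jan 1994 | 16.0 years |
| Denmark, biosimilar | 26 Mar 2014 | 1 Jan 1994 | 20.2 years |

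The Swedish HP-hMG figure equals the 3-year minimum baseline that section 9.1.1 promises, so that minimum is met. It is a floor on observation, and it does not establish that a cycle is a woman's first. For an index date of 31 December 2019 the Swedish look-back has grown to 13.0 years.

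**2. Who is missed.** A woman is misclassified only if every earlier cycle was before 2007. The gap since her last cycle must then be longer than the look-back: more than 3 years for an index date on 1 January 2010, 5 years on 1 January 2012 and 7.5 years on 20 June 2014. Any Q-IVF cycle between 2007 and the index date identifies her. If long gaps are rarer than short ones, the error is concentrated in the early years of the HP-hMG comparison.

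**3. What the drug register adds.** The SPDR starts in July 2005. At 1 January 2010 it gives 4.5 years, 1.5 years more than Q-IVF. The protocol does not use it to define *first-ever*.

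**4. Possible size (assumed inputs).** The documents give neither the misclassified share *m* nor the difference *d* between those women's MC-CLBR and that of true first-cycle women. The shift in one cohort's rate is *m* × *d*.
- With *m* = 0.5% and *d* = 10 points: 0.005 × 10 = 0.05 point.
- With *m* = 5% and *d* = 20 points: 0.05 × 20 = 1.0 point.

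As a count, 75% of the 18,000 Swedish reference-product women in Table 2 is 13,500. Then 0.005 × 13,500 ≈ 68 and 0.05 × 13,500 = 675 women. These counts are upper bounds for the assumed shares, because Table 2 counts all users of the drug and not first-ever patients.

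The shift in the between-cohort difference is *m*₁*d*₁ − *m*₀*d*₀. It is close to zero if the cohorts are alike, and reaches the full 0.05 to 1.0 point only if one cohort alone is affected. For scale, section 9.5 gives 1.5 points as the detectable difference in this comparison.

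**The case against.** The strongest reply is that the protocol already signals observed rather than lifetime history. Section 9.1.1 counts the first five cycles observed in the IVF registers and promises only a 3-year minimum baseline. Section 9.2.3 says that the length of the baseline varies. The 2010 start is a reasoned balance of power against heterogeneity. This stands in part. However, the observed-cycle wording belongs to the five-cycle limit, while Set 8, section 9.7.3.3 and Table 8 analysis 3 all say *first-ever*. Section 9.7.1 leaves modifications of the analysis sets to the SAP, but the label, opening date and data source are fixed here.

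A reader might infer that the propensity score cannot correct for the missing history at all. The documents do not support that. Section 9.2.3 uses all available register data for covariates. Parity is a propensity-score candidate and the Swedish birth register goes back to 1973. Swedish patient-register history runs from 1998, and the SPDR shows dispensing from July 2005. Earlier failed cycles and true rank remain largely invisible, so adjustment is partial.

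A reader might also infer that the Swedish odds ratio is biased in a known direction. The documents do not show this either. Women returning after earlier failures and women returning for a sibling may differ in prognosis, so even the sign of *d* is open. A route to unequal misclassification exists: Table 1 does not make calendar year a propensity-score candidate, and section 9.9.2 expects prescribing to vary over time. Its effect is not quantified.

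Finally, the Danish comparison is less clean than 16 years suggests, since section 9.9.2 reports suspected under-capture in 1994 to 2005. Countries are also analysed separately, with heterogeneity assessed before any pooling.

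**Conclusion.** The point holds, within narrow limits. On the protocol's own dates, Swedish Set 8 in the HP-hMG comparison cannot deliver first-ever cycles. It delivers cycles that are first observed since 2007, with 3.0 years of look-back at opening. Women whose earlier cycles were all before 2007 enter a primary-outcome analysis at the wrong rank, and the protocol neither screens for them nor lists the limitation.

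The scope is one country, one comparison and mainly the early years; the biosimilar comparison is little affected. The effect on the odds ratio cannot be derived from the documents. Under the assumed ranges above, one cohort's rate would move by 0.05 to 1.0 point, and the contrast by less if both cohorts are affected alike. This is a definition to correct and a limitation to state. It is not evidence that the Swedish result is unsound, and it does not require the main analysis to start later.

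**What to change.** 1. Keep 1 January 2010 as the main start. For Sweden, define *first-ever* as no earlier Q-IVF stimulation since 2007 and no SPDR dispensing from July 2005 to December 2006 that indicates an IVF stimulation, meaning a gonadotropin together with a GnRH analogue. Requiring both is meant to keep women treated earlier only with ovulation induction or IUI. Section 14.3.3 already lists the drug codes.
2. Add to Table 8 a sensitivity analysis opening Swedish Set 8 on 1 January 2012 for the HP-hMG comparison, which gives at least 5 years of Q-IVF look-back.
3. State in section 9.9 that Swedish cycle rank and IVF history, including the count behind exclusion 1, are left-truncated at 2007.

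LBR and CLBR keep their 2010 start. The cost is protocol wording, one extra analysis run, a small number of excluded women and lower precision in the sensitivity analysis. No new register is needed. The screen cannot reach cycles before July 2005.

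The size of the 2012 set should not be read off Table 2. Taking 8 of 10 accrual years gives 0.75 × 18,000 × 0.8 = 10,800 and 0.75 × 17,000 × 0.8 = 10,200 women. These are upper bounds, because they count all drug users, assume even accrual and subtract nothing for the screen.

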The overall study period will be between 2010 and 2020. Different study period starts will be applied depending on which two drugs are being compared. For the comparison between rhFSH-alfa reference product and HP-hMG, the study period will start 1 January 2010 for both countries. This date is selected to ensure the study is sufficiently powered while also reducing heterogeneity in patient management over time. Changes that have occurred over time include moving towards vitrification rather than slow freezing for embryo cryopreservation and hence also moving from cleavage stage to blastocyst embryo transfers, elective single embryo transfers rather than double embryo transfers, and antagonist protocols rather than agonist protocols. For the comparison between rhFSH-alfa reference product and rhFSH-alfa biosimilar products, the study period will start 26 March 2014 for Denmark and 20 June 2014 for Sweden. These are the earliest dates when a rhFSH-alfa biosimilar product (Bemfola) received reimbursement status in each country. For

Sweden, where the IVF register is updated annually and has a lag time of approximately two years (see Section 9.4.2), inclusion of women undergoing IVF/ICSI treatment may end on 31 December 2019, depending on data availability at the time of data extraction. No such general restriction will be applied for Denmark, as the IVF register is updated monthly. In terms of follow-up of IVF/ICSI treatment and pregnancy outcomes, the study will end on 31 December 2020 (or last available date) for each country. Specifically, for the main analyses of the primary objective (LBR, CLBR and MC-CLBR) and secondary objective 4 (TTLB), a minimum follow-up period of 1 year has been chosen to allow sufficient time to achieve (at least) one live birth and a reasonable number of complete cycles for reliable estimates of live birth rates. Hence, the corresponding analyses are restricted to cycles initiated on or before 31 December 2019 (Sets 1 and 5 in Table 5). The minimum follow-up period will be extended to 2 years in a sensitivity analysis to explore the potential effect this has on the estimated MC-CLBR and TTLB (see sensitivity analysis 3 in Table 8).

To reduce possible bias linked to confounding by baseline characteristics, inverse probability of treatment weighting (IPTW), based on propensity scores (PS) (22), will be used to balance the distribution of potential confounders across the study cohorts.

Figure 1. Study design

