9.7.1 Analysis Sets

To address the study objectives, analysis sets will be constructed based on the study outcomes as defined in Section 9.1.2. To allow for a sufficient time period to assess the outcomes after the initiation of a stimulation cycle, the analysis sets will be restricted to outcome-specific time periods. For the analysis sets, the following outcome-specific time periods are applied: 1 year after the stimulation cycle initiation for LBR, CPR, OPR, MC-CLBR and TTLB; 1 year after the stimulation cycle and linked FET initiation for CLBR, CCPR, COPR, pregnancy loss, multiple pregnancy and treatment-associated costs; 1.5 months after the stimulation cycle initiation for oocyte retrieval and embryos cryopreserved per initiated stimulation cycle, and cycle cancellation; 1 month after the stimulation cycle aspiration for oocyte retrieval and embryos cryopreserved per aspirated stimulation cycle; 4 months after stimulation cycle initiation for OHSS; 3 months after last embryo transfer for implantation. Fresh and frozen embryo transfers will be assessed by using all fresh and frozen embryo transfers done by the end of the study period (31 December 2020).

The analysis sets and their use for the study objectives and outcomes are defined in Table 5. The use of analysis sets will be described in the statistical analysis, and any needed specific modifications or restrictions on the analysis sets needed for the analysis of the study objectives will be further described in the SAP.

Table 5. Description of analysis sets

Analysis set	Description of the analysis set	Study objective(s)	Study outcome measure(s)
Set 1	Stimulation cycles with drug of interest initiated on or before 31 December 2019	Primary objective	LBR
		Secondary objective 1	CPR
			OPR
Set 2	Stimulation cycles with drug of interest and linked FET cycles initiated on or before 31 December 2019	Primary objective	CLBR
		Secondary objective 1	CCPR
			COPR
		Secondary objective 5	Pregnancy loss
		Secondary objective 6	Multiple pregnancy
Secondary objective 9	Treatment-associated costs		
Set 3	Stimulation cycles with drug of interest initiated on or before 15 November 2020 ⁺	Secondary objective 2	Oocytes retrieved per initiated stimulation cycle
			Embryos cryopreserved per initiated stimulation cycle
			Utilizable embryos per initiated stimulation cycle
		Secondary objective 7	Cycle cancellation

Analysis set	Description of the analysis set	Study objective(s)	Study outcome measure(s)

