3	Minimum duration of follow-up for assessment of MC-CLBR and TTLB	The main analyses of the MC-CLBR and TTLB each uses a minimum of 1 year of follow-up and includes women who had initiated their first-ever stimulation	1 year is considered sufficient to achieve at least one live birth and a reasonable number of complete cycles for reliable estimates of the MC-CLBR in view of previous studies considering up to 9 (20) and 8 (21) stimulation cycles for the estimation of cumulative live birth rates with at least 1.5 and 2 years of follow-up, respectively.	Minimum follow-up period extended to 2 years, thus restricting the analysis to women who had initiated their first-ever stimulation cycle on or before 31 December 2018.	The effect of extending the minimum follow-up period on the conservative and optimal estimates of the MC-CLBR and on TTLB will be explored. The analysis of each outcome will otherwise be repeated as described in 9.7.3.3 and 9.7.3.4.

No.	Topic	Main analysis		Sensitivity analysis	
		Method	Justification	Alteration to method	Justification
		cycle on or before 31 December 2019.			
4	CLBR	The main analysis does not consider the possible impact of oocyte yield on CLBR.	Oocyte yield is not considered in the stratified analysis.	CLBR in the first, second and third stimulation cycle will be estimated by the number of oocytes retrieved in the first cycle (cycle rank expressed as observed in the study period).	Oocyte yield is known to be positively associated with CLBR (20,40,41). The effect of oocyte yield in the first cycle will be explored for the CLBR. Otherwise the analysis will be repeated as described in 9.7.3.3 and 9.7.3.4, although rates will only be reported for the IPTW-weighted cohorts.

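### If Swedish Q-IVF data end on 31 December 2019, Set 8 keeps that same day as its entry cut-off, so 2019 starters lack the stated year of observable treatment for MC-CLBR and TTLB

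*Protocol*

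**What the plan says.** Protocol 9.7.1 sets outcome-specific windows, among them "1 year after the stimulation cycle initiation for LBR, CPR, OPR, MC-CLBR and TTLB". Section 9.1.1 explains the choice: "a minimum follow-up period of 1 year has been chosen to allow sufficient time to achieve (at least) one live birth", and also "a reasonable number of complete cycles for reliable estimates of live birth rates". The minimum is therefore meant to cover treatment as well as birth. On the end of follow-up, 9.1.1 says "the study will end on 31 December 2020 (or last available date) for each country".

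Table 5 defines Set 8 as "Women who initiated their first-ever stimulation cycle with drug of interest on or before 31 December 2019".

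For Sweden, 9.1.1, 9.2.1 (footnote) and 9.2.3 allow that inclusion may have to end on 31 December 2019. Section 9.4.2 describes Q-IVF data as "becoming available approximately 2 years after the treatment was performed", adding that more frequent reporting from 2020 may shorten the lag. Swedish extraction is planned for January to February 2022 (Section 6).

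The contingency is written under Table 5: "Should data on initiated cycles from the Swedish Q-IVF be available only through 31 December 2019, this analysis set will be adjusted". The adjustment keeps the day and month and changes the year to 2019. Sets 3 to 7 carry the mark; Sets 1, 2 and 8 do not.

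Section 9.7.3.3 assumes, for the main MC-CLBR, that women not seen to return after a failed attempt during the study period had no live birth. Section 9.7.3.5 ends TTLB follow-up at end of study, among other events. Table 8, analysis 3, reads "Minimum follow-up period extended to 2 years, thus restricting the analysis to women who had initiated their first-ever stimulation cycle", with 31 December 2018 as the date.

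**The concern.** Set 8 depends most on later treatment records. MC-CLBR and TTLB count births from all linked FET cycles and from up to five stimulation cycles, and in Sweden those cycles are identified in Q-IVF. If Q-IVF stops on the last day of entry, a woman whose first cycle began late in 2019 has almost no chance of a recorded FET or second stimulation. Her absence reflects where the data stop, yet the main MC-CLBR reads it as not returning and scores no live birth.

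The other unmarked sets are less exposed. Set 1 needs only the birth after the fresh transfer, and Set 2 already limits linked FET cycles to those started by 31 December 2019.

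At stake is a primary outcome in one of two countries, and the sensitivity analysis meant to test follow-up length. The shortfall may also differ between cohorts. Section 9.9.2 says biosimilar use is relatively heavier late in the period, and Table 1 lists calendar year as a baseline characteristic but neither as a propensity-score candidate nor for additional adjustment. The planned weighting would not be expected to remove a difference in entry dates.

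**Working it through.** **1. The protocol's windows, with data to 31 December 2020.** Formula: data end minus cut-off (Table 5), against the window in 9.7.1.

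| Set | Cut-off | Months available | Window stated |
|---|---|---|---|
| 1 and 8 | 31 Dec 2019 | 12.0 | 12 |
| 3 | 15 Nov 2020 | 1.5 | 1.5 |
| 4 | 30 Nov 2020 | 1.0 | 1 |
| 5 | 31 Aug 2020 | 4.0 | 4 |
| 7 | 30 Sep 2020 | 3.0 | 3 |

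All reproduce. The cut-offs were built from a 31 December 2020 data end.

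**2. Swedish Q-IVF ending 31 December 2019.** Sets 3 to 7 move back a year and keep their windows. Set 8 does not move:
- first cycle on 1 January 2019: 364 days of observable treatment;
- first cycle on 31 December 2019: 0 days;
- mean for 2019 starters under even entry: 364/2 = 182 days, about 6.0 months.

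Every 2019 starter falls short of one year of observable treatment.

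**3. Sensitivity analysis 3.** From 31 December 2018 to 31 December 2019 is 365 days: 1 year, not 2.

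**4. The existing note applied to Set 8.** Same day and month, year 2019, gives 31 December 2019, which is already its date. Adding the mark would change nothing.

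**5. What survives.** Section 9.4.2 says the Swedish birth register usually has the previous calendar year in December, so births in 2020 should be available before extraction in January 2022. Births from cycles started by the end of 2019 largely remain visible. FET and stimulation cycles started in 2020 do not.

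**6. Share affected, assuming even entry.**
- HP-hMG comparison, 1 January 2010 to 31 December 2019: 365/3,652 = 10.0%.
- Swedish biosimilar comparison, 20 June 2014 to 31 December 2019: 365/2,021 = 18.1%.

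**7. Precision if 2019 starters are dropped.** Criterion from 9.5: lower 95% limit of the OR above 1, comparator rate 50%. Smallest d with ln[p/(1−p)] > 1.96 × √{1/[n1·p(1−p)] + 4/n0}, where p = 0.5 + d. As a check with equal cohorts, d = 2.0 points needs 4,801 women per cohort (Table 3: 4,600) and d = 1.5 points needs 8,536 (Table 3: 8,000), so this formula is slightly stricter than Table 3. Inputs are the Table 2 counts of women at 75% eligibility.
- HP-hMG: 13,500/12,750 gives 1.22 points; less 10%, 12,150/11,475 gives 1.28 (stated 1.5).
- Biosimilar: 8,250/7,500 gives 1.57 points; less 18%, 6,760/6,145 gives 1.73 (stated 2.0).
- If 30% to 40% of biosimilar women started in 2019 (an assumption, with 18% in the reference cohort): 1.8 to 1.9 points.

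Table 2 counts users, whereas Set 8 holds only first-ever starters, so true cohorts will be smaller. The comparison with the stated figures uses the protocol's own counts on both sides.

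**The case against.** The strongest reply is that the problem is conditional. Truncation is a possibility, 9.4.2 says the lag may shorten, and 9.7.1 leaves further modifications of the sets to the SAP. The condition stands and limits the point. The deferral is a weaker answer, because the protocol itself writes this contingency into Table 5 and the rule as written leaves Set 8 where it is.

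Second, a reader might infer that one-year follow-up is lost altogether. The document does not support that: birth follow-up of observed cycles largely survives through the birth register. Only the treatment part of the 9.1.1 justification fails.

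Third, a reader might infer that every Set 8 analysis treats these women as failures. Only the conservative MC-CLBR does. TTLB censors them, and the optimal estimate in sensitivity analysis 2 does not score them as failures, though it does not repair the main analysis.

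Fourth, the plan would partly expose the problem. With Q-IVF ending in 2019, sensitivity analysis 3 at 31 December 2018 is the set the main analysis should have used, and 9.9.2 already concedes possible downward bias for biosimilars. Both are true, but the headline estimate would still come from the wrong set, and no true 2-year check would remain.

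Fifth, it is tempting to attach a bias in percentage points. That needs the MC-CLBR lost per truncated woman and each cohort's share of 2019 starters, and the document gives neither. Under even entry the shares are equal, so unequal shares would not arise as a source of bias.

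Last, the contrast with Denmark should not be pressed. The Danish IVF register is updated monthly, but the Danish birth register lags 13 months and extraction is planned for August to September 2021, so complete 2020 births are not assured there either. Pooling is optional and preceded by a heterogeneity review.

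**Conclusion.** The point holds as a conditional error in the contingency rule. If Q-IVF treatment data end on 31 December 2019, Swedish Set 8 does not deliver the stated 1-year minimum for treatment. Women starting in 2019 have 0 to 364 days of observable FET and repeat cycles. Those without an observed birth are counted as non-returners in the conservative MC-CLBR and censored early in TTLB, and sensitivity analysis 3 delivers half its labelled minimum.

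Under even entry, about 10% of the Swedish HP-hMG comparison and about 18% of the biosimilar comparison are affected. The biosimilar cohort may have a larger share because its use is later, which would add to the downward bias that 9.9.2 already admits for biosimilars. Neither the size of that effect nor a difference between cohorts can be calculated from the document. The point should be settled before the Swedish analysis.

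**What to change.** Add a separate note to Table 5 and Table 8; extending the existing mark to Set 8 would leave its date unchanged. If Q-IVF treatment data end on 31 December 2019, close Swedish Set 8 at 31 December 2018 and Swedish sensitivity analysis 3 at 31 December 2017.

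Better still, state the rule generally: entry to Set 8 at least 1 year (2 years in sensitivity analysis 3) before the last date of complete IVF-register data in that country.

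The cost is one note and a date parameter, plus about one year of Swedish entrants lost for MC-CLBR and TTLB. Intervals widen slightly: at the protocol's counts, the detectable difference goes from 1.22 to 1.28 points for HP-hMG and from 1.57 to 1.73 for biosimilars, within the stated 1.5 and 2.0. If Q-IVF data through 2020 are available at extraction, the current dates stand.
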